### 8.2 Sample size estimate

A total of 260 participants receiving SOC treatment will be randomised 1:1 to treatment with anifrolumab or placebo.

The treatment effect of anifrolumab vs placebo measured by BICLA response at Week 52 will be estimated using the Bayesian robust MAP prior approach with borrowing from the pooled global phase III studies (study 05 and study 04). The sample size is calculated based on the criterion of having greater than ■■■ posterior probability that anifrolumab 300mg is effective compared to placebo (difference in BICLA response rates at Week 52 greater than 0).

In study 05, a difference of 17.0% in BICLA response rates at Week 52 was observed for anifrolumab 300 mg compared with placebo (47.1% vs 30.2%, 95% CI 7.2, 26.8; nominal  $p < 0.001$ ). In study 04, participants treated with anifrolumab 300 mg had a statistically significant higher BICLA response rate at Week 52, compared with participants in the placebo group (47.8% vs 31.5%; difference 16.3%, 95% CI 6.3, 26.3;  $p=0.0013$ ). The pooled BICLA response rates for anifrolumab 300 mg and placebo groups based on study 05 and study 04 are 47.5% and 30.8%, respectively. Results for BICLA responses at Week 52 in study 05 and study 04 trials are also listed in [Table 8](#).

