**Table 8 BICLA response rates at Week 52 in study 05 and study 04**

		Response Rates BICLA at 52 weeks	Treatment difference (95% CI) BICLA at 52 Weeks
Study 05	Placebo	55/184 (30.2%)	-
	Anifrolumab 300mg	85/180 (47.1%)	17.0% (7.2%, 26.8%)
Study 04	Placebo	57/182 (31.5%)	-
	Anifrolumab 300mg	86/180 (47.8%)	16.3% (6.3%, 26.3%)
Pooled study 05 & study 04	Placebo	112/366 (30.8%)	-
	Anifrolumab 300mg	171/360 (47.5%)	16.6% (9.7%, 23.6%)

The current study mirrors study 04's design with the same target population (moderate to severe SLE patients), treatment groups and randomization ratio. The primary endpoint BICLA response at Week 52 is also evaluated with the same definition as study 05 and study 04. Given the robust response rates in study 05 and study 04, the pooled BICLA response rates at Week 52 in will be used as an informative prior for the response rates of anifrolumab 300 mg and placebo groups in the Asian population. The robust MAP prior approach (Schmidli et al, 2014) will be adopted to partially extrapolate the pooled response rates of study 05 and study 04 to the Asian population. The informative prior will be robustified with a prior weight, where the weight represents the a priori degree of relevance of the pooled response rates of study 05 and study 04 to the Asian population. With a level of extrapolation ( ), and the assumed proportions of BICLA response rates 47.5% and 30.8% in the anifrolumab 300 mg and placebo groups respectively (based on the pooled study 05 and study 04), 130 participants/arm yields chance of having have greater than posterior probability that anifrolumab is effective compared to placebo, i.e., the lower limit of credible interval of treatment difference is greater than 0 in a Bayesian framework (power: ). In mathematical notation, it can be written as

$$P(\pi_1 - \pi_0 > 0 | data) >$$

where  $\pi_1$  and  $\pi_0$  represent the underlying response rates of anifrolumab 300 mg and placebo groups respectively. Under the assumptions of no treatment difference (30.8% vs 30.8%), 130 participants/arm and prior weight will control the probability of having greater than posterior probability of efficacy at approximately (one-sided type I error: ). Expecting screen failure rate of 50%, approximately 520 participants shall be screened to obtain the required number of randomised participants.

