#### **8.5.3.2 Analysis method for immunogenicity variables**

Anti-drug antibodies to anifrolumab will be summarized using descriptive statistics at each visit by treatment group. ADA titres-time profiles of anifrolumab by treatment group will be generated. The impact of ADA on PK and PD will be assessed. The potential association of ADA with safety and efficacy will be explored.

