Where necessary (e.g., for subgroup analysis based on stratification factors), the model factors will be reduced. If not stated otherwise, the subgroup analysis will be suppressed if any of the sub-populations in any treatment group will consist of less than 25 participants.

Table 2 Summary of Analyses

Statistical category	Endpoint	Population	Intercurrent event strategy	Population level summary (analysis)	Details in section
Objective 1: To evaluate the effect of anifrolumab compared to placebo on disease activity as measured by the difference in the proportion of participants achieving BICLA response at Week 52.					
Primary Analysis of the Primary Endpoint	BICLA response at week 52	Asian adults with moderate-to-severe SLE	Composite strategy where RM/PEOT/Death=NR	Difference in proportions between interventions (Bayesian analysis), Week 52	4.2.1.4
Supportive Analysis of the Primary Estimand	BICLA response at week 52	Asian adults with moderate-to-severe SLE	Composite strategy where RM/PEOT/Death=NR	Difference in proportions between interventions (CMH), Week 52	4.2.1.5
Supportive Analysis of the Primary Estimand	BICLA response at week 52	Asian adults with moderate-to-severe SLE	Composite strategy where RM/PEOT/Death=NR	Odds ratio between interventions (Bayesian analysis), Week 52	4.2.1.6
Supplementary Analysis of the Primary Endpoint – targeting impact of PEOT due to different reasons	BICLA response at week 52	Asian adults with moderate-to-severe SLE	Composite strategy where RM, Deaths, PEOT due to lack of therapeutic response = NR Hypothetical strategy where PEOT due to COVID lockdown = MAR Treatment policy where PEOT not due to lack of therapeutic response or COVID lockdown = ignored	Difference in proportions between interventions (CMH; multiple imputation), Week 52	4.2.1.7.1
Supplementary Analysis of the Primary Endpoint - targeting the impact of PEOT	BICLA response at week 52	Asian adults with moderate-to-severe SLE	Composite strategy where RM/Death=NR Treatment policy where PEOT = ignored	Difference in proportions between interventions (CMH), Week 52	4.2.1.7.2

Statistical category	Endpoint	Population	Intercurrent event strategy	Population level summary (analysis)	Details in section

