4.2.1.8 Subgroup Analyses

To explore the uniformity of the detected overall treatment effect on the primary endpoint (i.e., only for the primary estimand excluding the supplementary and sensitivity analyses), subgroup analyses may be performed for the following factors:

- Region (mainland China versus not mainland China)
- SLEDAI-2K score at screening (<10 points versus ≥ 10 points)
- OCS dose at baseline (<10 mg/day versus ≥ 10 mg/day prednisone or equivalent)
- Sex (male versus female)
- Age (≥ 18 to <65 versus ≥ 65 years)
- Onset of disease (adult versus pediatric onset)
- BMI (≤ 28 versus >28 kg/m²)
- IFN 4-gene test (high versus low)
- ADA Result (positive at any time, negative, persistently positive, positive with titer $>$ median of maximum titer)
- Baseline anti-dsDNA, C3 and C4 (at least one positive/abnormal, all negative/normal)

Treatment effect is estimated by the stratified CMH model. A forest plot reporting response rates, estimated differences with its 95% CI for treatment derived by the stratified CMH model is presented overall and by subgroups.

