4.2.3.6 Subgroup Analyses

The subgroup analyses will be performed for the following stratification factors excluding the subgroup OCS dose at baseline (< 10 mg/day versus ≥ 10 mg/day prednisone or equivalent), i.e.

- Region (mainland China versus not mainland China)
- SLEDAI-2K score at screening (< 10 points versus ≥ 10 points).

The analysis methods are the same as described above for the maintained OCS reduction endpoint in Section 4.2.3.4.

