4.7 China Subpopulation Analyses

Approximately 80% of the participants are estimated to be recruited from mainland China. The efficacy and safety in China subpopulation (defined as all participants from sites in mainland China) were analyzed to facilitate a benefit-risk assessment for regulatory submission in China.

Efficacy are summarised for the China subpopulation, which consists of all randomized participants from sites in mainland China in the Full Analysis Set as defined in Section 3.2.2. Selected key analyses will be conducted and stratified analyses will not include the stratification factor region for the China subpopulation. These analyses are considered descriptive/supportive only, therefore no significance testing will be performed.

Safety and tolerability are summarised for the China subpopulation, which consists of all dosed participants from sites in mainland China in the Safety Analysis Set as defined in Section 3.2.3.

The PK data is summarised for the China subpopulation, which consists of all dosed participants from sites in mainland China in the Pharmacokinetic Analysis Set as defined in Section 3.2.4.

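### The 25-per-arm suppression rule will very probably remove the ADA subgroup and the region subgroup on the OCS endpoint, and the ADA comparison would not answer the ADA question even if it were run

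*SAP*

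**What the plan says.** SAP 4.2 gives a default for subgroup analyses: "the subgroup analysis will be suppressed if any of the sub-populations in any treatment group will consist of less than 25 participants". On the natural reading, one small level in one arm removes the analysis of that factor. The default yields where the SAP says otherwise.

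**ADA.** SAP 4.2.1.8 lists, in permissive wording, the factors for the primary endpoint. They include "ADA Result (positive at any time, negative, persistently positive" and a fourth level for positive titres above the median of the maximum titre. The treatment effect in each level comes from the stratified CMH method. SAP 4.2.8.1 defines persistent positivity as a form of treatment-induced ADA and takes the titre cut-off as the median among participants with treatment-induced ADA. Protocol 8.5.3.2 states: "The potential association of ADA with safety and efficacy will be explored". SAP 4.2.8.4 names subgroup analyses as the possible route for efficacy.

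**Region on the OCS endpoint.** SAP 4.2.3.6 says: "The subgroup analyses will be performed for the following stratification factors excluding the subgroup OCS dose at baseline", which leaves region and screening SLEDAI-2K. SAP 4.2.3.4 restricts the analysis to participants with baseline OCS of at least 10 mg/day. SAP 4.7 adds: "Approximately 80% of the participants are estimated to be recruited from mainland China". Protocol 8.2 fixes the size: "A total of 260 participants receiving SOC treatment will be randomised 1:1 to treatment with anifrolumab or placebo".

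**The concern.** The size rule and the list of analyses appear to have been written separately. For ADA, the rule asks for sizeable groups of ADA-positive participants in an arm that never receives anifrolumab. If it bites, the protocol's commitment to explore ADA and efficacy is left with no specified efficacy analysis. If it does not bite, the quantity estimated is the wrong one. For region, a firmly worded analysis of a key secondary endpoint would probably not appear. Region is a randomisation factor, and whether the effect is similar inside and outside mainland China is an obvious question for this trial.

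**Working it through.** **Inputs.** 260 randomised 1:1 (Protocol 8.2); 25 per level per arm (SAP 4.2); about 80% mainland China (SAP 4.7); ADA definitions (SAP 4.2.8.1). The documents give no ADA rate and no share with baseline OCS of at least 10 mg/day, so both are varied as assumptions.

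**The plan's own counts.** 260/(1 - 0.50) = 520 screened, as Protocol 8.2 states; 260/2 = 130 per arm. Each subgroup level therefore needs 25/130 = 19.2% of each arm.

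**ADA.** Let q be the share of an arm that is positive, with the count Binomial(130, q).

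| Assumed q | Expected positives per arm | P(at least 25 in one arm) |
|---|---|---|
| 5% | 6.5 | below 0.001% |
| 10% | 13 | 0.1% |
| 15% | 19.5 | 11% |
| 20% | 26 | 62% |

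These are chances for one arm and for positivity of any kind. The rule needs both arms, and the persistently positive level is a subset. The high-titre level lies above a median taken among treatment-induced positives, so it holds at most about half of them. Reaching 25 then takes about 50 per arm, or 50/130 = 38%. This treats the level as drawn from treatment-induced positives. P(at least 50 in an arm) is about 1 in a million at q = 20% and 2.4% at q = 30%.

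**What the ADA comparison estimates.** A CMH difference within the positive level sets ADA-positive anifrolumab participants against ADA-positive placebo participants. Positivity in placebo cannot be a response to anifrolumab, and positivity after baseline arises after randomisation. The contrast is between two differently selected groups. It does not show whether anifrolumab participants with ADA respond less well than those without.

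**Region, OCS endpoint.** Non-mainland participants: 0.20 × 260 = 52, or 26 per arm, before the OCS restriction. To keep 25 per arm, 25/26 = 96% of them must have baseline OCS of at least 10 mg/day. Inclusion criterion 7 admits participants without OCS and OCS monotherapy from 7.5 mg/day, and randomisation is stratified at 10 mg/day, so a share near 100% is not what the plan expects. With qualifying share s, the total is Binomial(260, 0.20s):

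| Assumed s | Expected per arm | P(suppressed), arms evenly split | P(suppressed), arms independent |
|---|---|---|---|
| 50% | 13 | above 99.9% | above 99.9% |
| 70% | 18.2 | 98.8% | 99.6% |
| 80% | 20.8 | 91% | 97% |

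Region and OCS dose are both stratification factors, so the evenly split column is the closer description. The result is sensitive to the mainland share: at 70% mainland there are 39 per arm, and s = 25/39 = 64% gives an expected 25.

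**Region, primary endpoint.** The expected 26 per arm is just above the cut-off. With evenly split arms, P(total below 50) is about 35%.

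**Precision if shown.** Protocol 8.2 uses "the assumed proportions of BICLA response rates 47.5% and 30.8% in the anifrolumab 300 mg and placebo groups respectively". At 26 per arm, the 95% half-width is 1.96 × √(0.475×0.525/26 + 0.308×0.692/26) = 0.261, about ±26 percentage points. No rates are assumed for the OCS endpoint, so this is a guide only.

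**The case against.** The best reply has several parts.

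- **The rule is a default.** The SAP uses permissive wording for the primary-endpoint list but firm wording in 4.2.2.6, 4.2.3.6 and 4.2.4.8. The firm wording can be read as the stated exception. That reading is possible, but nothing says so, and a programmer following 4.2 would suppress the output. The ambiguity stands.
- **ADA is optional in SAP 4.2.1.8, and any-time positivity includes baseline positives.** Placebo positives are therefore not excluded, and omission would follow the SAP. Both points are right. Neither helps the persistently positive or high-titre levels, and neither makes the comparison informative. The PK and PD summaries by ADA status, and the subject-level information on ADA-positive participants, do not replace an efficacy analysis.
- **A reader might infer that the planned enrolment cannot meet the rule for ADA, sex or age.** The documents do not support that. They give no ADA rate, age distribution or planned sex mix; the 12:1 ratio in Protocol 1.1 is background epidemiology for the childbearing years. Sex and age are probably suppressed, but they are optional, and a minimum size that removes them is a defensible choice.
- **A reader might infer that region on the primary endpoint will be lost.** It is more likely produced than not. The 61% suppression obtained with unconstrained arm splits does not describe a trial with blocks stratified by region.
- **Mainland China has its own analyses under SAP 4.7.** This is true, and it leaves the non-mainland side of the OCS comparison uncovered.

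**Conclusion.** The point holds for two analyses. The ADA factor in SAP 4.2.1.8 is very unlikely to survive the rule at ADA rates up to about 20%. More importantly, its design would not measure the association that Protocol 8.5.3.2 says will be explored. Region on the OCS endpoint is suppressed with probability 91-97% at an assumed 80% qualifying share and above 99.9% at 50%, given about 80% mainland recruitment, while SAP 4.2.3.6 commits to it. These figures rest on assumed ADA and OCS shares and on an approximate recruitment estimate, so they show high probability, not impossibility. Region on the primary endpoint is borderline, at about 35%. The subgroups are descriptive, and neither the primary Bayesian analysis nor the main key secondary estimates are affected.

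**What to change.** 1. **ADA.** Remove ADA from the treatment-effect subgroups in SAP 4.2.1.8; the subgroup list in Protocol 8.5.4 does not contain it. Tabulate BICLA response at Week 52 by ADA category within the anifrolumab arm, with the overall placebo rate as reference, and point SAP 4.2.8.4 to that table. Label it descriptive and non-randomised, because ADA status after baseline is not assigned.
2. **Region.** State in SAP 4.2 that the region subgroups in 4.2.1.8, 4.2.2.6, 4.2.3.6 and 4.2.4.8 are exempt from the 25-per-arm rule. Show n and response rates (or flare rates) by arm, with an estimate and CI, unstratified where strata are too small. Label the results descriptive.

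The cost is SAP wording and a few table rows before unblinding, with no new data. The drawback is imprecision: about ±26 points at 26 per arm, wider still once the OCS restriction applies if the rates are similar.

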4.2.1 Primary Endpoint

4.2.1.1 Definition

The primary endpoint used to evaluate the effect of anifrolumab compared to placebo on disease activity is the difference in the proportion of participants achieving BICLA response at Week 52, where a participant is a BICLA responder if all the following criteria are met:

- Reduction of all baseline BILAG-2004 A to B/C/D and baseline BILAG-2004 B to C/D, and no BILAG-2004 worsening in other organ systems, as defined by ≥ 1 new BILAG-2004 A or ≥ 2 new BILAG-2004 B.
- No worsening from baseline in SLEDAI-2K, where worsening is as defined as an increase from baseline of >0 points in SLEDAI-2K
- No worsening from baseline in participants' lupus disease activity, where worsening is defined by an increase ≥ 0.30 points on a 3-point PGA VAS

In addition, time to onset of a BICLA response that is sustained up to Week 52 is assessed. A participant is considered to have achieved BICLA response sustained up to Week 52 if a response is achieved at Week 52 with "time to" defined as the first timepoint from Study Day 1 where a BICLA response is achieved and maintained through Week 52.

4.2.1.2 Derivations

The following participants are considered as having met the criteria for BILAG and PGA VAS, respectively.

- Participants with no BILAG A or B at baseline and no worsening in any organ systems where worsening is defined as: ≥ 1 new BILAG-2004 A or ≥ 2 new BILAG-2004 B,
- Participants with a baseline PGA VAS score > 2.7 .

4.2.1.3 Handling of Dropouts and Missing Data

If any of the criteria cannot be evaluated at any visit up to Week 52 (e.g., due to missing values), the data for that criterion is imputed using LOCF and BICLA response is derived based on the complete data. This applies only once. Missing data after LOCF will be imputed as non-responder. For example, if any of the Week 52 criteria data is missing and Week 48 data is not missing, the missing Week 52 criteria data will be imputed using the corresponding Week 48 data. Otherwise, the participant is defined as a BICLA non-responder at Week 52.

4.2.1.4 Primary Analysis of Primary Endpoint

The intercurrent events: PEOT, RM and death are unfavourable outcomes. Therefore, participants with these intercurrent events will be non-responders from the time such events occur.

For the primary analysis, Bayesian inference will be performed for the estimation of the treatment difference on BICLA response at Week 52 in the Asian population. A robustified mixture prior approach will be adopted to partially extrapolate the response rates of anifrolumab 300mg and placebo groups in the pooled study 05 and study 04, to this study. This robustified mixture prior approach closely follows the MAP prior approach as described by Schmidli et al (2014).

Informative prior

First, an informative prior is constructed by pooling results from study 05 and study 04. We assume the number of responders in the placebo and anifrolumab 300mg groups of study 05 and study 04, denoted as Y_{hk} , $h = 1, 2$; $k = 0, 1$, follow binomial distributions,

$$Y_{hk} \sim \text{Bin}(N_{hk}, \pi_{hk}),$$

where $h = 1, 2$ represent study 05 and study 04, $k=0, 1$ represent placebo and anifrolumab 300mg groups, N_{hk} , $k = 0, 1$ represent the number of participants in the placebo and anifrolumab 300mg groups respectively in study 05 and study 04 respectively, and π_{hk} , $k=0, 1$ represent the probability of being a responder in placebo and anifrolumab 300mg groups respectively. Let Y_k , $k = 0, 1$ be the number of responders and N_k , $k = 0, 1$ be the number of participants in the placebo and anifrolumab 300mg groups in the current study. Therefore Y_k follows a binomial distribution with parameter π_k , $k = 0, 1$. The informative prior for π_k , is chosen as beta distribution with parameters (a_k, b_k) , i. e.

$$\hat{p}_{Hk}(\pi_k | Y_{hk}, h = 1, 2) = \text{Beta}(a_k, b_k), k = 0, 1$$

where $\text{Beta}(a, b)$ is the beta function

$$\text{Beta}(a, b) = \int_0^1 t^{a-1} (1-t)^{b-1} dt,$$

and (a_k, b_k) are to be estimated from the results of study 05 and study 04. Given the homogeneous response rates from study 05 and study 04 as shown in [REDACTED] 8 of the CSP v3.0, we take $(a_0, b_0) = (112, 254)$ and $(a_1, b_1) = (171, 189)$ from the pooled results from the placebo and anifrolumab 300mg groups respectively. The choice of (a_k, b_k) can be interpreted in a way where a_k represents the number of responders and $a_k + b_k$ represents the number of participants in that group.

We construct a robustified mixture prior for π_k , as

$$\hat{p}_{HRk}(\pi_k) = w * \hat{p}_{Hk}(\pi_k) + (1 - w) * Beta(1,1), k = 0, 1$$

where \hat{p}_{Hk} is the estimated informative prior, and the second component $Beta(1,1)$ is the noninformative, flat prior. The weight term, w is the prior (initial) weight to place on the source data in the mixture distribution above. It can range between 0-1 and represents the *a priori* degree of relevance the source data has to the target population.

At CDL, the mixture prior distribution \hat{p}_{HRk} is then updated with observed data on the target population, i.e. our current trial data results. Importantly, the prior weight w , is also updated to posterior weight. This accounts for any conflict between the informative prior based on the source data and the observed data. Therefore, in the posterior estimation, the source data can be further discounted if results in target population are observed to be very different than results of source data.

This produces posterior distributions of the response rates in Asian population that borrows from what is already known about the response rates in study 05 and study 04. By the conjugate properties of beta-binomial distribution, the posterior distribution can be estimated as

$$\hat{p}_{HRk}(\pi_k|Y_k) = \tilde{w} * Beta(a_k + Y_k, b_k + N_k - Y_k) + (1 - \tilde{w}) * Beta(1 + Y_k, 1 + N_k - Y_k), k = 0, 1$$

where \tilde{w} is the updated mixture weight, N_k and Y_k are the numbers of responders after applying the intercurrent event strategy as mentioned in Section 4.2.1.4 The MCMC analysis will be used to estimate the posterior distribution of the parameters in the model.

Analyses

██████████ prior weight ██████████ will be used for the primary analysis for BICLA response at Week 52. Posterior median estimates for the treatment difference and the corresponding ██████████ credible intervals will be presented. Posterior probabilities of efficacy (treatment difference greater than 0), i.e. $P(\pi_1 - \pi_0 > 0 | data)$, will also be estimated and compared with a number of thresholds including ██████████. Results across a range of prior weights will be also presented as for the primary endpoint.

4.2.1.5 Supportive Analysis of the Primary Estimand - Stratified Cochran-Mantel-Haenszel (CMH) approach

This estimand answers a clinically relevant question comparing the proportion of participants able to both complete the study treatment and to achieve adequate response without further medication being required. The summary measure is the difference in the proportion of subjects achieving BICLA response at Week 52 using the FAS, comparing the anifrolumab to the placebo groups.

The null hypothesis is that the proportion of participants achieving BICLA response on anifrolumab is equal to that on placebo. The alternative hypothesis is that the proportion of participants achieving BICLA response on anifrolumab is not equal to that on placebo, i.e.,

H_0 : difference in proportion achieving BICLA response (anifrolumab vs Placebo) = 0

H_a : difference in proportion achieving BICLA response (anifrolumab vs Placebo) \neq 0

The proportion of participants achieving BICLA response in the anifrolumab treatment group will be compared to that in the placebo group using a CMH (Clowse et al, 2017) stratified by:

- SLEDAI-2K score at screening (<10 points versus \geq 10 points).
If different measurements are available for re-screened participants, the value at rescreening will be used.
- Randomization (Day 1) OCS dose (<10 mg/day versus \geq 10 mg/day prednisone or equivalent). For the classification, the derived OCS dose rounded to 1 decimal place will be used.
- Region (mainland China versus not mainland China)

SLEDAI-2K score at Screening and Randomization (Day 1) OCS strata will be derived programmatically from the data recorded in the database. Region (mainland China versus non-mainland China) stratum will be taken as recorded at randomization by the Interactive voice/web response system (IXRS). Strata with low counts will be pooled with adjacent strata prior to the analysis. If a substratum within the non-mainland China region stratum has less than 20 participants (in the pooled treatment group), then all non-mainland China region strata will be pooled together. If a sub-stratum within the mainland China region stratum has less than 20 participants (in the pooled treatment group), then within the mainland China region stratum the SLEDAI-2K score <10 points sub-strata will be pooled together and the SLEDAI-2K score \geq 10 points sub-strata will be pooled together. If any of these two sub-strata within the mainland China region stratum still has less than 20 participants (in the pooled treatment group), then all China region sub-strata will be pooled together. If all not mainland China region sub-strata are pooled together and all mainland

China region sub-strata are pooled together and any of these strata has less than 20 participants (in the pooled treatment group) then all strata are pooled together.

The analysis can be described as follows:

- A. There are n_{ij} participants in each stratum, where i is the stratum, and j is the treatment group. The number of participants achieving BICLA response is x_{ij} . The proportion of participants achieving BICLA response is denoted as $p_{ij} = x_{ij} / n_{ij}$.
- B. For each stratum, the difference in proportion of participants achieving BICLA response is calculated as $d_i = p_{iA} - p_{iP}$, where A and P denote the different treatment groups (anifrolumab and placebo, respectively).
- C. Weights for each stratum, w_i , are calculated as $n_{iP} * n_{iA} / (n_{iA} + n_{iP})$. The weighted difference is calculated as:

$$WD = \frac{\sum w_i d_i}{\sum w_i}$$

- D. The standard error (SE) of the weighted difference under the null hypothesis is given by:

$$SE = \sqrt{\frac{\sum [w_i^2 \text{Var}(d_i)]}{(\sum w_i)^2}}$$

- E. For deriving the CI for the weighted difference in proportions, a correction will be applied to the variance, providing a CI with more accurate coverage. This will be applied to all strata and is derived as follows.

$$\text{Var}(d_i) = \frac{p_{iA}^* (1 - p_{iA}^*)}{n_{iA}} + \frac{p_{iP}^* (1 - p_{iP}^*)}{n_{iP}} \text{ with}$$

$$p_{ij}^* = \frac{x_{ij} + 2}{n_{ij} + 4}$$

The 95% CI can be generated using the weighted difference $\pm z_{0.975} * SE$.

The value of the test statistic is calculated as $\frac{WD}{SE}$. The p-value from the two-sided test of no difference in treatment groups is calculated as $2(1 - \text{Prob}(|\frac{WD}{SE}|))$, where $\text{Prob}()$ is the distribution function of the standard normal distribution.

- F. The 95% CI for the weighted proportion $\frac{\sum w_i p_{ij}}{w}$ in a treatment group j can be generated using a normal approximation and assuming independence between strata, where p_{ij}^* are used as above.

$$S_{ij}^2 = \text{Var}(p_{ij}) = \frac{p_{ij}^* (1 - p_{ij}^*)}{n_{ij}}$$

$$SE_j^2 = \frac{\sum w_i^2 S_{ij}^2}{w^2}, w = \sum w_i$$

The 95% CI can be generated using the weighted proportion $\pm z_{0.975} * SE_j$.

If the resulting lower or upper limit is $<0\%$ or $>100\%$, it will be set to 0% or 100% , respectively.

The estimated treatment effect (i.e., the difference in response rate for anifrolumab versus placebo), corresponding 95% CI, and 2-sided p-value for the difference at Week 52 will be presented. In addition, the estimated response rate (weighted proportion) and the corresponding 95% CI within each treatment group will be presented.

Longitudinal presentations of results over time (i.e., for each post-baseline visit up to Week 52) based on the same CMH analysis, with the corresponding 95% CI, will be created. Line plot will be created accordingly.

4.2.1.6 Supportive Analysis of the Primary Estimand – Bayesian Borrowing based on odds ratio

The proportion of participants achieving BICLA response at Week 52 in the anifrolumab treatment group will be compared to that in the placebo group using a logistic regression model with treatment arm and the stratification factors as covariates. The results of the analyses will be presented using odds ratio (OR), together with associated 95% CI.

Bayesian inference will be performed for the estimation of the OR on BICLA response at Week 52 in the Asian population. A robust mixture prior approach will be applied to partially extrapolate the treatment effect observed in the global study to this study. This approach was reviewed and evaluated for belimumab intravenous infusion in children 5 to 17 years of age with SLE (FDA: BLA 125370/s-064 and BLA 761043/s-007).

The pooled result of Study 04 and Study 05 is used as an informative prior distribution on the OR of BICLA response rate in this study. The log odds ratio $\log(OR)$ for BICLA response is assumed normally distributed. Let θ_p be the $\log(OR)$ for this study and let $p_a(\theta_p)$ be the informative prior for θ_p . Therefore,

$$p_a(\theta_p) \sim N(\log(2.03), 0.15^2)$$

where 2.03 is the observed OR for BICLA at Week 52 from the pooled global data for anifrolumab versus placebo and 0.15^2 is the variance of the OR represented as the standard error squared.

The robust mixture prior θ_p is constructed, as

$w * p_a(\theta_p) + (1 - w) * N(0, \sigma_{NonInf}^2)$ where $N(0, \sigma_{NonInf}^2)$ represents the non-informative prior assuming an OR = 1 representing no difference in the treatments resulting

in a mean of 0 [i.e., $\log(1) = 0$] and a standard deviation consistent with information from one participant. The term w reflects the prior amount of weight given to the informative component of the prior and $1 - w$ is the remaining weight that is given to the non-informative component.

Once this data collection is complete, this mixture prior distribution is updated with the observed study results, and inference is conducted on the resulting posterior distribution. Importantly, the prior weight, w , is updated based on the observed data in order to account for any conflict between the informative component of the prior based on the global data and the observed data. Therefore, in the posterior estimation, additional weight can be given to informative component of the prior if Asian are observed to be similar, or the informative component can be discounted if results in Asian are observed to be very different. This method produces a posterior distribution of the treatment effect in Asian that dynamically borrows from what is already known about the treatment effect in the pooled result of Study 04 and Study 05.

Prior weight ranging from $w = 0$ to $w = 100\%$, with a step size of 5%, will be used for the analysis for BICLA response at Week 52. Posterior median estimates for the OR, the corresponding [REDACTED] credible intervals and posterior probabilities of efficacy (treatment difference greater than 0), i.e. $P(\text{OR} > 1 | \text{data})$, will be presented.

